procedure is to minimize any potential exposure to infection as a result of participating in this study. The study's team will follow CDC-recommended cleaning and disinfection guidelines to ship and retrieve the prototype VR headset (that is, the bone-conduction headphones along with the goggles sans the iPhones, which the participants can keep as part of participating in the study).

The proposed study will not discriminate based on gender, sexual orientation or race. Participants will be recruited from a pool of children at participating clinics and educational facilities independent of the above-mentioned aspects. There are no exclusion criteria based on gender, sexual orientation, or race.

Because data prior studies strongly support no significant differences of clinical or public health importance in intervention effect between subgroups, then sex/gender and/or race/ethnicity will not be recorded as subject selection criteria.

Children with a medically documented history of seizure disorder will be excluded from the study. According to Carnegie Mellon University Entertainment Technology Center (2019), individuals with a history of seizure disorder should avoid using virtual reality media.

Study procedures / research method

Due to health and safety concerns associated with the COVID-19 pandemic, the feasibility procedures will be conducted through a HIPAA-compliant telehealth platform. The subjects' caregivers or parents will help measure the impact of two pieces of technology: the 3D VR-integrated headset with bone-conduction and the 2D tablet-based application.

In order to prevent the spread of pathogens among large groups of subjects, the number of participants has been reduced from 30 to 10. Ten ASD students between the ages of 4 and 8 will be recruited to participate in a 14-sessions-long study that will utilize the integrated VAST application. The subjects will each receive a different piece of technology: one group of five will receive a 3D VR-integrated VAST prototype, while the other group of five will receive a 2D VAST version on a tablet. Sessions will be held twice a week with each lasting approximately 30 minutes (i.e. 30 minutes +/- 5 minutes).

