Secondary	Change in Response Rate to Treatment Stimuli	Seven weeks--each subject participated in the study twice a week over a 7-week period for a total of 14 sessions. The first and last sessions (session #1 and session #14) were reserved for pre-test and post-test language sample collection and assessment.	Response rate gain measured whether there were any significant changes in how often children responded to pre- and post-testing stimuli after having received treatment between the iPad Pro and VR goggles groups.

Risk / Safety Information

Participants in this study will face little to no harm, risks, or discomfort. Participants will undergo the Impact Metrics within their own homes via a HIPAA-compliant telehealth video stream in order to minimize the risk of COVID-19 exposure. Additionally, all equipment affiliated with the study will be cleaned and disinfected, following CDC guidelines, prior to the subjects receiving the equipment.

Participants will face no greater than minimal risk during the implementation of Aim 3's Impact Metrics. Each assessment session will last 30 minutes (+/- 5 minutes) twice per week. During the course of each assessment session, the participants will interact with known adults to decrease the chances of them feeling uncomfortable. As the software is

100% virtual, no adverse effects, risks, or discomforts are anticipated, other than what the participant may experience looking at a typical tablet screen or wearing VR goggles. Additionally, the hardware used in this study is designed to be worn for long periods of time with minimal to no discomfort.

However, the research team recognizes that it is possible that some participants may experience feelings of frustration, embarrassment, or fatigue through participation due to the amount of sensory integration within the particular treatment. It is recognized that the issue of sensory and stimulus overload is common in children with ASD. Children on the spectrum sometimes experience inability to focus or distress when exposed to a surplus of stimuli. Avoiding this overload is not a matter of simplifying learning materials but rather managing the perceptual load children are exposed to.

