sensory and stimulus overload is common in children with ASD. Children on the spectrum sometimes experience inability to focus or distress when exposed to a surplus of stimuli. Avoiding this overload is not a matter of simplifying learning materials but rather managing the perceptual load children are exposed to.

Should any Adverse Events (AEs), Serious Adverse Events (SAEs) — injuries, seizures, or emotional distress — and Unanticipated Problems Involving Risks to Subjects or Others occur, a session will be ceased immediately and a report submitted to the IRB within 48 hours by the on-site researcher. If an SAE were to occur — such as an injury or seizure — staff will contact emergency medical services to ensure the subject's safety. Staff will receive training in communication and behavioral de-escalation strategies, whose aim is to reduce subjects' exposure to emotional distress. The PI and Co-investigator, both certified autism specialists, will be responsible for implementing the training.

All stimuli and engagement topics will be thoroughly vetted to reduce any discomfort on the part of the participant. Research staff will be advised to immediately cease engagement upon any visual sign of participant discomfort. Participants will only participate in the study as a supplement, and not a replacement, of prescribed or existing therapies.

Monitoring and reporting of Adverse Events/Serious Adverse Events

The research team will monitor subjects' exposure to adverse events/SAE throughout the study. For example, we will ensure that the methods of data collection do not invade the privacy of students, parents, teachers, or schools. We will monitor participation and responses to oversee and reduce potential feelings of frustration or embarrassment. Additionally, all children using the VR headsets will be required to sit so as to avoid

falling or suffering other injuries that might occur from standing or walking while wearing the headsets.

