There are no events that would preclude a participant from continuing the intervention beyond withdrawal of assent or consent. As detailed in the Protections Against Risk above, the study presented no greater than minimal risk to participants. Trials will be stopped upon any visual observance of discomfort of the participant by the educator or trained professional (as detailed in the Protections Against Risk above). Data will be reported from all sites upon session completion – compliance and monitoring will be ensured by an on-site researcher who will collect session data. Further data security measures are detailed above in Collaborating Sites.

Any IRB and/or ISM/DSMB actions will be reported to the NIH within 72 hours of occurrence by the project PI [name].

Study Oversight

Data and safety will be monitored per NIH guidelines by project PI and IRB. Individual responsible for monitoring are:

1. [name] (project PI). [name] will ensure data security on a bi-weekly basis. Her position as CEO of iTherapy will include the monitoring of all data acquired from this study. She will ensure that all staff are adequately trained in the study protocol.
2. [name] (Co-Investigator). [name] will ensure safety on-site on a weekly basis. As the Chief Operations Officer at iTherapy, he is qualified to ensure data and safety during data collection.
3. IRB will ensure protocol adherence to acceptable safety practices.

Data Management

[Who will be collecting, analyzing the data? Do you plan to have an independent data analysis? Data retention (i.e. how long so you plan to maintain records for this study). Include statistical analysis plan (if applicable)]

Data formats — data will be stored in commonly-used file formats (e.g., .csv for survey data, .mp3 for audio files, .mov for screen recordings). There are no applicable metadata standards that will be applied to these data.

Dissemination — all data generated in this SBIR Phase I project is considered proprietary. A project report will be made available partial and/or aggregated form, upon request, to the intervention developers. A subset of the project report will be made available, upon request, to partner school districts or other organizations who assisted in recruiting participants.

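### The protocol says no event bars continuing, so a VR-arm child may return to the headset after a first on-study seizure without medical review or a re-check of the seizure exclusion

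*Combined protocol and SAP*

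**What the plan says.** Four parts of the combined protocol bear on this.

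- **Entry (Subject Selection).** "Children with a medically documented history of seizure disorder will be excluded from the study". The reason given is that "individuals with a history of seizure disorder should avoid using virtual reality media".
- **Response to an event (Risk / Safety Information).** The adverse events foreseen are "injuries, seizures, or emotional distress". If one occurs, "a session will be ceased immediately and a report submitted to the IRB within 48 hours by the on-site researcher". For a serious event such as a seizure or injury, staff also call emergency medical services.
- **Continuation (Monitoring and reporting of Adverse Events/Serious Adverse Events).** "There are no events that would preclude a participant from continuing the intervention beyond withdrawal of assent or consent". The same paragraph says trials stop when discomfort is seen, and refers back to a section called Protections Against Risk.
- **Oversight and consent.** Study Oversight says "Data and safety will be monitored per NIH guidelines by project PI and IRB", with a weekly safety check by the co-investigator. IRB Review / Ethics / Informed Consent has parents present throughout and able to stop at any time. The child may also stop, and teachers or health professionals watch for signs of discomfort, which end the session.

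**The concern.** The protocol treats seizure as the hazard specific to VR when it decides who may enter. Once a child is enrolled, it gives a general continuation rule with one exception, withdrawal of assent or consent. This is a stated rule, not a missing detail, and on its face it covers seizure.

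At stake is whether a child aged 4 to 8 goes back into a headset after the kind of event the exclusion is meant to keep away from VR. Sessions take place in the home over telehealth, so the study team relies on what is written down. The protocol describes both lead investigators as certified autism specialists, and it gives nobody a medical role in deciding whether a child resumes.

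**Working it through.** The protocol gives no figure to reproduce on this point. The check is first textual, then a costing of the remedy.

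**Step 1. Is any safeguard a condition for using VR again after a seizure?**

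| Provision | Section | What it does | Condition for resuming? |
|---|---|---|---|
| Stop the session | Risk / Safety Information | Ends that session | No |
| Call emergency services | Risk / Safety Information | Deals with the event; may lead to an assessment | No; no link to permission to resume |
| IRB report within 48 hours | Risk / Safety Information | Informs the IRB, which could act | No; no reply has to be awaited |
| Stop on visible discomfort | Monitoring and reporting; IRB Review / Ethics | Ends the session (so worded in the ethics section) | No |
| Parent or child may stop | IRB Review / Ethics | Voluntary veto | No; not a medical review |
| PI, co-investigator and IRB oversight | Study Oversight | General; co-investigator check is weekly | No |
| Seizure exclusion | Subject Selection | Bars a documented history of seizure disorder | No re-check on study is described |

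No provision requires a hold, medical review or eligibility re-check before the next VR session.

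**Step 2. Timing.** Sessions are twice a week. If evenly spaced (an assumption), the gap is 7/2 = 3.5 days. The 48-hour report would then normally be due before the next session. Nothing makes that session wait for a response.

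**Step 3. What a hold would cost if one VR child had a seizure.**

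Inputs:
- 14 sessions over 7 weeks, with sessions 1 and 14 reserved for testing (Outcome Measures), leaving 14 − 2 = 12 intervention sessions.
- VR arm of 5 (Study Goals and Objectives; Study procedures), or 6/2 = 3 if the stated total of 6 (Subject Selection) is split equally, which is an assumption.
- VR-arm sessions: 5 × 12 = 60, or 3 × 12 = 36.
- Hold of 1 to 3 weeks (assumed) at 2 sessions a week: 2 to 6 sessions.
- Permanent stop after session 2: sessions 3 to 13 are lost, which is 11.

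| Scenario | Sessions lost | Share of child's 12 | Share of arm, 5 children | Share of arm, 3 children |
|---|---|---|---|---|
| Hold, 1 week | 2 | 2/12 = 17% | 2/60 = 3.3% | 2/36 = 5.6% |
| Hold, 3 weeks | 6 | 6/12 = 50% | 6/60 = 10% | 6/36 = 17% |
| Permanent stop after session 2 | 11 | 11/12 = 92% | 11/60 = 18% | 11/36 = 31% |

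The child affected is 1/5 = 20% or 1/3 = 33% of the arm. A permanent stop later in the schedule loses fewer sessions. With no seizure, the loss is zero.

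**The case against.** The best defence is that the plan does a good deal after a seizure. Three steps are mandatory: stopping the session, calling emergency services and reporting to the IRB. Every session is monitored and recorded. A parent is present and holds a veto, and the IRB could intervene. An unexamined return to VR is therefore less likely than the continuation sentence alone suggests. This stands, and it rules out the inference that nothing has to happen before the next session. What remains is that none of these steps governs resumption.

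A second defence is that the exclusion is worded as exclusion from the study, not only at entry. A child newly diagnosed with seizure disorder arguably meets it already. That also has force. A reader might infer that continuing after any seizure contradicts the exclusion, but the text does not support this, because one seizure is not by itself a documented history of seizure disorder. The gap is the first, undiagnosed seizure, where no re-check is required to find out whether the exclusion now applies.

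Third, the continuation paragraph relies on Protections Against Risk, a heading that does not appear in the supplied text. Risk / Safety Information is read here as that section. If a separate section exists and sets a resumption rule, the point falls away.

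Finally, the protocol rates the study as no more than minimal risk and excludes known seizure disorder. That bears on how likely the event is. It does not settle what to do after an event for which the protocol itself plans.

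**Conclusion.** The point holds for on-study seizures and VR use. The continuation rule lets a VR-arm child resume after a first seizure without medical review or a re-check of the exclusion. This is in tension with the reason given for that exclusion, though it does not contradict the exclusion itself.

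The risk cannot be sized because the documents give no seizure rate. At most 5 children are exposed to VR, or 3 on an equal split of 6. The percentages in the working are costs of the remedy, not estimates of harm.

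A reader might extend the point to the tablet arm, to injuries, or to a duty on the IRB to clear each child. The documents do not support this. The stated reason concerns VR alone, the tablet arm uses no headset, no comparable argument is made for injuries, and the IRB is given no child-level clearance role.

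The conclusion rests on reading Risk / Safety Information as the section cross-referenced. The cost range rests on the assumed hold of 1 to 3 weeks and on the uncertain arm size.

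**What to change.** Replace the continuation sentence in the adverse-event monitoring section with:

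> Withdrawal of assent or consent ends participation. After any on-study seizure, VR use is held until a documented medical review and a re-check of the seizure exclusion clear resumption, and the outcome is reported to the IRB. A child who newly meets the exclusion stops VR permanently but may remain for post-test assessment.

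Keeping the child for post-test matters in so small an arm, because the primary measures are pre-to-post changes and the session 14 assessment is still wanted.

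If sessions are still running, this takes a short amendment, IRB review and a staff briefing, with no added participants or routine procedures. The price is missed treatment, and only if a seizure occurs: 17% to 50% of the child's intervention sessions under the assumed hold, and 92% under a permanent stop after session 2.

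Parts of the protocol are written in the past tense, so sessions may already be complete. In that case, report whether any seizure occurred and how continuation was handled, and carry the rule into any follow-on protocol.

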Aim 1: Develop a beta product VR-based VAST platform. Currently, the alpha product VAST program utilizes filmed mouths enunciating words and phrases in a 2D setting. Developers will code the VR mouths and the graphic design for all linguistic elements. Coding will comprise of C++ & Unreal Engine 4 where unreal engine utilizes a node-based language called *Blueprints Visual Scripting*. Further attributes of Unreal Engine include a skeletal animation system combined with higher polygon models. In addition to VR programming, the *Dolch Vocabulary list* will be integrated into the system as a base word list consisting of frequently used English words. Within the list are 220 easily recognizable service words including nouns and non-nouns which target the kindergarten-through-third grade age group. *Deliverable: The alpha product 2D software will be developed into a 3D VR environment to ensure maximum optimization of the product for client use.*

Aim 2: Develop hardware prototype. We will compare the utility of combining off-the-shelf VR goggles & Bone Conduction (BC) headphones with a 3D printing of a single cohesive unit. The strength of the BC headphones will be tested alongside standard headphones to determine if they provide optimal functionality. After testing each option, the product with the highest rate of efficacy will be used to create the integrated prototype. *Deliverable: Functional hardware prototype.*

4.2.c. Interventions

Type	Name	Description
Behavioral (e.g., Psychotherapy, Lifestyle Counseling)	VR-based VAST platform	The VR-incorporated prototype, 3D video-modeled VAST application
Behavioral (e.g., Psychotherapy, Lifestyle Counseling)	2D video modeling	VAST application using 2D video recordings and no hardware prototype

Aim 3: Demonstrate feasibility of VR-based VAST platform. We will pilot test the VR VAST app on 6 children with ASD. The recruited population will consist of 6 ASD children between the ages of 4 and 8 who will be recruited to participate in a 14-sessions-long study that will utilize the VR-integrated VAST application. The subjects will each receive a different piece of equipment: one group of five will receive a 3D VR-integrated VAST prototype, while the other group of five will receive a 2D VAST on a tablet. Sessions will be held twice a week with each lasting approximately 30 minutes (i.e. 30 minutes +/- 5 minutes).

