Three main metrics will be measured during the pilot study: *Percentage of Correctly Transcribed Words Using ASR, Articulation Accuracy, and Mean Length of Utterance (MLU)*. These metrics will show whether there has been improvement in the participant’s functional language abilities, and oral motor coordination skills. They will be

analyzed by several trained staff members who will observe each recorded and monitored session.

Subject Selection

Recruiting: Subjects will be recruited by contacting (e.g. email or telephone) teachers and professionals (e.g. speech-language pathologists and behaviorists) who work with children with autism, aged 4 to 8. The research team will reach out to school administrators, teachers, and specialists through the iTherapy network of contacts to recruit eligible K-2 students diagnosed with ASD and their teacher or specialist. The VR-based VAST platform is designed for use with early elementary school-aged students (grades K-2). In order to conduct the intervention and gather data that would be useful for further development of the product, the research study must include early elementary school students.

In order to recruit enough children within the study's target population and to encourage retention, the study team will use online advertising via social media and other platforms (e.g. Craigslist) to reach participants. All participants will be given an Apple device (iPhone 6 for VR or refurbished iPad mini for 2D) for participating in the study and a free download of InnerVoice (valued at \$99.99), an iOS AI-powered communication app that uses video self-modeling, designed and sold by iTherapy.

Number of participants: 6

Inclusion/Exclusion criteria: All participants will be recruited via campaigns posted on social media and/or other platforms: parents/guardians will be provided consent forms and all information regarding inclusion/exclusion criteria.

Children **under the age of 18** will be recruited and all protections mandated by NIH policy afforded to them.

In order to protect participants and their families from COVID-19 exposure, participants will undergo Aim 3's procedures within their homes: the subjects' data will be collected using a HIPAA-compliant telehealth video-streaming platform. The goal of this

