Primary	Change in Percentage of Correctly Transcribed Words Using Automatic Speech Recognition	Seven weeks--each subject participated in the study twice a week over a 7-week period for a total of 14 sessions. The first and last sessions (session #1 and session #14) were reserved for pre-test and post-test language sample collection and assessment.	15-minute pre- and post-testing was performed using speech recognition software and transcribed by a licensed speech pathologist. Differences pre- and post-intervention were compared across groups and within groups.
Primary	Change in Articulation Accuracy	Seven weeks--each subject participated in the study twice a week over a 7-week period for a total of 14 sessions. The first and last sessions	Change in % of correct phonemes in each attempted stimulus

		(session #1 and session #14) were reserved for pre-test and post-test language sample collection and assessment.	
Primary	Change in Mean Length of Utterance (MLU)	Seven weeks--each subject participated in the study twice a week over a 7-week period for a total of 14 sessions. The first and last sessions (session #1 and session #14) were reserved for pre-test and post-test language sample collection and assessment.	Participants (aged 4 to 8 years) were given a pre- and post-test 15-minute language sample. MLU was calculated for tests and gain from pre-test to post-test was compared.
Secondary	Parent Perceptions of Communication Changes Resulting from Study Participation	Seven weeks--each subject participated in the study twice a week over a 7-week period for a total of 14 sessions. The first and last sessions (session #1 and session #14) were reserved for pre-test and post-test language sample collection and assessment	Parent observations -- perceptions of changes in their children's motor-speech, behavioral, and social communication skills after having participated in the study

Secondary	Change in Type-Token Ratios	Seven weeks--each subject participated in the study twice a week over a 7-week period for a total of 14 sessions. The first and last sessions (session #1 and session #14) were reserved for pre-test and post-test language sample collection and assessment.	A type-token ratio measures the total number of unique words in a given segment of language.

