While all efforts will be made to keep data confidential, there is a small chance that participation in research may cause a loss of privacy. There is also a small risk of data loss and misuse or breach of private information. No physical, social, cultural, financial, legal, or other risks to subjects are expected from this study.

The data will be kept for ten years beyond the life of the project before all the files are destroyed, to allow for future longitudinal studies. While the data are kept for these additional years, the same storage protocols described above will be followed.

For the different group, electronic images (e.g., pdf), spreadsheets, and database files

Statistical Design and Power

We have used the following formula to calculate power and size of an experiments where there are >2 means:

$$n = 2 \left(\sigma \frac{z_{1-\alpha/(2\tau)} + z_{1-\beta}}{\mu_A - \mu_B} \right)^2$$

$$1 - \beta = \Phi \left(z - z_{1-\alpha/(2\tau)} \right) + \Phi \left(-z - z_{1-\alpha/(2\tau)} \right) \quad , \quad z = \frac{\mu_A - \mu_B}{\sigma \sqrt{\frac{2}{n}}}$$

Assumptions:

Power, $1-\beta$: 0.08

Type I error rate, α : 0.05

$\mu_A = 1$

$\mu_B = 2$

$\sigma = 1$

$\tau = 1$

Source: Chow S, Shao J, Wang H. 2008. Sample Size Calculations in Clinical Research. 2nd Ed. Chapman & Hall/CRC Biostatistics Series. page 71.

MLU, SIS, and articulation rate between groups will be tested using an ANOVA with pairwise comparisons.

may be created from paper-based field notes as researchers code data into an electronic form and de-identify (anonymize) response records. Data will then be protected as mentioned above.

IRB Review / Ethics / Informed Consent

As participants are children, all additional protections for children involved as subjects in research will be observed. We do not expect the study to involve greater than minimal risk and will obtain IRB approval of adequate provisions for soliciting the assent of the children and the permission of their parents or guardians.

The study involves children with ASD. Informed written consent from parents/guardians of the child participants is required prior to beginning any part of the study. Parents/guardians will be present at all times during the testing and will be able to stop

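### The stated power of 0.08 is unusable (probably 0.80 was meant), and no power is given for the reduced size of 10 or 6 children although between-group tests remain planned

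*Combined protocol and SAP*

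**What the plan says.** All references are to the combined protocol and SAP.

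- **Statistical Design and Power.** The section opens with "We have used the following formula to calculate power and size of an experiments where there are >2 means". It gives a sample-size formula and a matching power formula. The listed assumptions are power 0.08, type I error 0.05, means 1 and 2, SD 1 and τ = 1. It prints no resulting n. The planned test follows: "MLU, SIS, and articulation rate between groups will be tested using an ANOVA with pairwise comparisons".
- **Study procedures / research method.** To limit the spread of infection, "the number of participants has been reduced from 30 to 10", in two groups of five.
- **Study Goals and Objectives, Aim 3.** "We will pilot test the VR VAST app on 6 children with ASD". The same paragraph still describes two groups of five: "while the other group of five will receive a 2D VAST on a tablet".
- **Subject Selection.** "Number of participants: 6".
- **Outcome Measures.** For the speech-recognition primary outcome: "Differences pre- and post-intervention were compared across groups and within groups". The response-rate secondary outcome looks for significant changes after "treatment between the iPad Pro and VR goggles groups".

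**The concern.** There are two separate defects.

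First, a design power of 8% is not a credible target, and the section's own formula turns it into less than one child per group. No other text corrects it.

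Second, whatever power was meant, the documents give none for the trial as it now stands. The power section is their only power statement, and it fits neither 10 nor 6 children. This gap would be the same with 0.80 printed. Correcting the digit alone could even mislead, since a reader would then see 80% power beside a trial of 6 or 10.

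What is at stake is how a null result is read. With so few children, a non-significant VR-versus-tablet comparison could easily be taken to show that the two formats perform alike, and the Intended Use of Data section says the results will guide further design of the product.

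**Working it through.** **Inputs** (Statistical Design and Power): α = 0.05, two-sided because the formula uses z at 1 − α/(2τ); τ = 1; |μA − μB| = 1; σ = 1. The standardised difference is therefore 1 SD.

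**1. Sample size by the plan's formula**

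n per group = 2 × [σ(z₀.₉₇₅ + z₁₋β)/(μA − μB)]², with z₀.₉₇₅ = 1.960.

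- Power 0.08: z = −1.405, sum 0.555, n = 2 × 0.555² = 0.62.
- Power 0.80: z = 0.842, sum 2.802, n = 2 × 2.802² = 15.70, so 16 per group and 32 in total.

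The 0.08 corresponds to none of the documented sizes (30, 10 or 6). With 0.80 the total of 32 is close to the superseded 30.

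**2. Power by the plan's formula**

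1 − β = Φ(z − 1.960) + Φ(−z − 1.960), with |z| = 1/√(2/n).

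| n per group | \|z\| | Power |
|---|---|---|
| 16 | 2.828 | 0.807 |
| 15 (total 30) | 2.739 | 0.782 |
| 5 (total 10) | 1.581 | 0.353 |
| 3 (total 6, equal split assumed) | 1.225 | 0.232 |

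**3. Allowing for an estimated SD**

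The plan's formula treats the SD as known, which is optimistic at these sizes. The table below uses the noncentral t distribution, two-sided 0.05, with n₁ + n₂ − 2 degrees of freedom (df). The half-width of the 95% CI is t₀.₉₇₅,df × √(1/n₁ + 1/n₂), taking the sample SD equal to the assumed SD.

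| Split | df | Power at 1 SD | Difference for 80% power | 95% CI half-width |
|---|---|---|---|---|
| 5+5 | 8 | 0.286 | 2.02 SD | 2.306 × 0.632 = 1.46 SD |
| 3+3 (assumed) | 4 | 0.159 | 3.07 SD | 2.776 × 0.816 = 2.27 SD |
| 2+4 (assumed) | 4 | 0.147 | 3.26 SD | 2.776 × 0.866 = 2.40 SD |

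The sample SD averages slightly below the true SD in small samples (factor 0.969 at 8 df, 0.940 at 4 df). The expected half-widths for normal data are therefore 1.41, 2.13 and 2.26 SD. A simulation of 400,000 runs gave the same powers to within 0.001 (0.287, 0.159, 0.147) and the same expected half-widths.

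**The case against.** The strongest reply is that this is a digit slip in a feasibility pilot. Nothing in the documents uses the 0.08 or an n derived from it. Aim 3 is called a pilot test of feasibility, infection control is openly given as the reason for going to 10, and the Hypothesis concerns improvement in VR users and not a contrast between formats. A pilot need not have 80% power, and the 1-SD effect has no units, outcome or source, so power figures built on it are only illustrative. The outcome tables are partly in the past tense. If the data were already collected, a power figure added now would be after the fact.

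Much of this stands. The slip alone is minor, no larger trial is called for, and the figures here cover only the two-group contrast, not change within the VR group. The link between 0.80 and the total of 30 is also conjecture: the formula gives 32, and no text ties 30 to it.

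It does not remove the second defect. The plan chose to include a power section and a between-group ANOVA, and leaves both beside sample sizes that the calculation does not describe. The detectable differences and interval widths, expressed in SD units, do not depend on the 1-SD assumption and lead to the same conclusion. If the data are already in, the intervals and the caution about null results are the parts that matter most.

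**Conclusion.** The concern holds on both counts and should be fixed. The printed power of 0.08 is wrong as written or at least unusable: it implies 0.62 children per group. That 0.80 was meant is the natural reading but remains an inference. Independently of that, no power or precision is stated for the current size, and the documents disagree on whether that size is 6 or 10.

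For the plan's illustrative 1-SD difference, power at 5 per group is 35% by the plan's formula and 29% with the t distribution. At 3 per group it is 23% and 16%. Reaching 80% power would take a true difference of 2.02 SD at 5+5 or 3.07 SD at 3+3. These figures assume one two-sided comparison at 0.05, normal data with equal variances and no dropout. The documents give no split for 6 children; a 2+4 split gives slightly worse results than 3+3.

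**What to change.** 1. Correct 0.08 to the intended power and state the n it gives (16 per group if 0.80).
2. Reconcile 6 with 10 and with the two groups of five, so that one size and one split appear throughout.
3. Add a paragraph with the figures for the actual size, for example:

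> The sample size was not set by this formula [sponsor to confirm the reason; infection control is given for the reduction from 30 to 10]. For a between-group difference of 1 SD (two-sided alpha 0.05, t distribution) the power is 29% with 5 per group [16% with 3 per group]; 80% power would require a true difference of about 2.0 SD [3.1 SD]. The 95% CI half-width, taking the sample SD equal to the assumed SD, is 1.46 SD [2.27 SD]. Between-group tests are exploratory and are reported with estimates and 95% CIs; a non-significant result is not evidence of no difference.

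If data collection has already finished, the paragraph should say when it was added.

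The cost is small: one paragraph and the consistency edits, with no change to enrolment or procedures. The sponsor must confirm the reason for the size and accept a less favourable stated figure. The exploratory label does change the standing of the across-group part of the primary comparisons, so it should be a deliberate decision and be carried into the outcome table.
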